**Frequently asked questions**

*I have had the flu and have therefore visited my doctor, who certified me unfit for work. Do I have to enter the drugs, the doctor visit, the time of sick leave and the time in which I was not able to carry out my housework?*

No, please only enter things, which are directly related to your disease. We do not want to include all treatments and expenses, you had due to other diseases.

*I cannot remember the exact information on the package of my drug. What should I enter?*

Please try to answer as exactly as possible. If you do not have the package of the drug for copying the name from it anymore, please enter the type of drug, e.g. beta blocker.

*I have not received the bill for my alternative practitioner visit yet. What should I do now?*

Please enter a question mark. Unless, from experience, you are quite sure how much the bill will be. In that case, please enter your estimate.

*Due to my ALS disease, I have had expenses, which I do not know where to put, because none of the tables seems to really apply to them. Where should I enter these expenses?*

Please enter all expenses, treatments and applications which you cannot clearly assign to any question, into the questionnaire. Please do not leave out anything that is related to your disease.

## VERSION HISTORY

Version	Date	History list
0.1	15 Nov 2021	Draft version for sponsor review.
0.2	22 Feb 2022	2 nd draft version for review
0.3	13 May 2022	Pre-final version
0.4	09 Dec 2022	Updated pre-final version
1.0	19 Dec 2022	Final, including changes in updated protocol version
1.1	01 Jun 2023	Updated version for review. Due to update protocol, updated CRF, additional derivations, and additional analyses.
2.0	22 Jun 2023	Final for signature
2.1	11 Sept 2023	Updated version for review. Use of new SAP template. Derivations added for NCS, added handling of mis-randomized patients not being treated (for ITT), removal of CTC-AE summaries, adding mapping of unscheduled visits.
3.0	14 Sept 2023	Final for signature
4.0	07 Dec 2023	Final for signature, changes for primary endpoint analysis and some additional clarification for the PP/ITT sensitivity analysis.

## LIST OF ABBREVIATIONS

8-OHdG	8-hydroxyguanosine
ADaM	Analysis Data Model
AE	Adverse Event
AESI	Adverse Event of Special Interest
ALS	Amyotrophic Lateral Sclerosis
ALSFRS-R	ALS Functional Rating Score – revised
ALSAQ-40	ALS Assessment questionnaire 40
ALT	Alanine transaminase
ANCOVA	Analysis of Covariance
aPTT	Activated partial thromboplastin time
AR(1)	First order Autoregression
AST	Aspartate transaminase
BDRM	Blind Data Review Meeting
BMI	Body Mass Index
BUN	Blood urea nitrogen
CAFS	Combined Assessment of Function and Survival
CDISC	Clinical Data Interchange Standards Consortium
CI	Confidence Interval
CK	Creatinine kinase
CS	Compound Symmetry
CSR	Clinical Study Report
CTCAE	Common Terminology Criteria for Adverse Events
CTL	Clinical Trial Lead
DM	Data Manager
DSMB	Data Safety Monitoring Board
ECAS	Edinburgh Cognitive and behavioural ALS Screen
ECG	Electrocardiogram
eGFR	Estimated Glomerular Filtration Rate
EQ-5D-5L	EuroQoL – 5 Dimensions – 5 Levels
FCS	Fully Conditional Specification
GGT	Gamma-glutamyl transpeptidase
GLM	Generalized Linear Model

HCT	Haematocrit
HGB	Haemoglobin
HHD	Hand-held dynamometer
HR	Heart Rate
ICE	Intercurrent Event
ICH	Internation Conference on Harmonisation
LDH	Lactate dehydrogenase
ITT	Intent-To-Treat
MAR	Missing At Random
MCAR	Missing Completely At Random
MedDRA	Medical Dictionary for Regulatory Activities
MiToS	Milano-Torino staging system
mITT	Modified Intent-To-Treat
MMRM	Mixed Model for Repeated Measures
NCS	Nerve Conduction Study
NFL	Neurofilament Light
P75 ECD	Extracellular domain of neurotrophin receptor p75
PDF	Portable Document Format
PEG	Percutaneous Endoscopic Gastrostomy
PK	Pharmacokinetic(s)
PM	Project Manager
pMI	Placebo Multiple Imputation
PNG	Portable Network Graphics
PP	Per Protocol
PT	Preferred Term
PTT	Prothrombin Time
QoL	Quality of Life
Q1	Lower quartile
Q3	Upper quartile
RBC	Red Blood Cells
RMST	Restricted Mean Survival Time
RTF	Rich Text Format
SAE	Serious Adverse Event
SAF	Safety analysis population
SAP	Statistical Analysis Plan

SAS	Statistical Analysis Software
SD	Standard Deviation
SDTM	Study Data Tabulation Model
SOC	System Organ Class
SVC	Slow Vital Capacity
TEAE	Treatment Emergent Adverse Event
VAS	Visual Analogue Scale
WBC	White blood cell
WHO	World Health Organisation

## 1 GENERAL

This Statistical Analysis Plan (SAP) describes in detail the methods and presentation of the data analyses which will be conducted for study FAB 122-CT-2001 by Certara. Any references to PK analyses in this SAP are under responsibility of the involved PK scientist from the client, and analysis details are therefore not specified in this SAP. This plan is written in agreement with protocol version 4.0, dated 24 May 2023, and blank CRF version 3.0, dated 21 June 2023, the relevant GCP-ICH guidelines and sponsor requirements.

Since a separate DSMB-SAP will be developed for the DSMB analyses, this full study-SAP is to be finalized prior to database lock and unblinding for study FAB 122-CT-2001.

The protocol and the (annotated) CRF are the primary source for this document, together with the relevant GCP-ICH guidelines. Furthermore, sponsor requirements for reporting will be taken into account. Additional changes or updates of those documents or requirements may result in a new version of the reporting/statistical analysis plan.

## 2 STUDY INFORMATION

### 2.1 Study Objective(s)

The primary objective of this study is to assess the effect of treatment with 100 mg of FAB122 on disease progression in patients with ALS.

The secondary objectives of this study are as follows:

- To evaluate the effect of treatment with FAB122 on survival
- To evaluate the safety and tolerability of FAB122
- To evaluate the effect of treatment with FAB122 on quality of life (QoL)
- To evaluate the effect of treatment with FAB122 on cognitive functioning
- To evaluate the pharmacokinetics (PK) of FAB122.

[figure not shown]
The exploratory objectives of this study are as follows:

- To evaluate the PK interaction of FAB122 and riluzole
- To explore and identify biomarkers that inform the statistical understanding of ALS and/or their therapeutic treatments.

### 2.2 Design of the Study

This is a multicenter, multinational, double-blind, randomized (2:1), placebo-controlled Phase III study to investigate the efficacy and safety of 100 mg FAB122 (former TW001) once daily as oral formulation in approximately 300 ALS patients (200 FAB122, 100 Placebo).

Patients will receive double-blind treatment up to a maximum of 72 weeks. The study is planned to continue until the last randomized patient has reached 48 weeks of follow-up (or has reached an intercurrent event) AND the first one third (100) of the randomized patients has reached 72 weeks of follow-up (or has reached an intercurrent event).

## 2.3 Study medication

Patients will receive 100 mg FAB122 or matched placebo for 48 or 72 weeks. Riluzole (100 mg/day or less) may be used as background (add-on) therapy, where patients should be on stable doses at the start of the study and for at least 30 days before the initiation of study drug.

## 2.4 Sample size

The sample size estimation is based on the primary endpoint: the change from baseline in ALSFRS-R score after 48 weeks. A difference of 3.0 points between FAB122 treatment arm and placebo is assumed with a (pooled) standard deviation of 7.5 and an allocation ratio of 2:1 (FAB122:Placebo). With these assumptions, a total sample size of 300 (200 patients on FAB122 and 100 on placebo) is needed to achieve 90% power to detect the difference of 3.0 points between the two treatment groups at a 5% (2-sided) level of significance.

For further details on the background of these assumptions, refer to the protocol.

## 2.5 Study assessments

	Screening	Baseline	Treatment period															
			V1 D1 W0	V2 D28 W4 ±3D	T1 D56 W8 ±4D	V3 D84 W12 ±3D	T2 D112 W16 ±4D	T3 D140 W20 ±4D	V4 D168 W24 ±7D	T4 D196 W28 ±7D	T5 D224 W32 ±7D	V5 D252 W36 ±7D	T6 D280 W40 ±7D	T7 D308 W44 ±7D	V6/EoT D336 W48 ±7D	V7 D420 W60 ±7D	V8  D504 W72 OR EoT 	
Administrative procedures																		
ICF	X																	
ICF for PK	X																	
In/exclusion criteria	X	X 																
Medical history	X																	
Prior/Concomitant medication			X-----X															
Randomization	X																	
Dispensing study medication/Compliance check	X*			X					X			X			X	X		
Clinical Procedures																		
Physical examination	X	X							X						X	X		
Weight	X	X							X						X	X		
Height	X																	
Vital Signs	X	X	X	X					X			X			X	X	X	
12-lead ECG	X	X							X						X	X	X	
Neurological examination 	X	X	X	X					X			X			X	X	X	
NCS 	X*		X	X					X									
(S)AE monitoring		X-----X																
Laboratory procedures																		

	Screening	Baseline	Treatment period															
			V1 D1 W0	V2 D28 W4 ±3D	T1 D56 W8 ±4D	V3 D84 W12 ±3D	T2 D112 W16 ±4D	T3 D140 W20 ±4D	V4 D168 W24 ±7D	T4 D196 W28 ±7D	T5 D224 W32 ±7D	V5 D252 W36 ±7D	T6 D280 W40 ±7D	T7 D308 W44 ±7D	V6/EoT D336 W48 ±7D	V7 D420 W60 ±7D	V8  D504 W72 OR EoT 	
Chemistry/Haematology 	X	X 	X		X				X			X			X	X	X	
Vitamin B6 monitoring 	X	X	X	X					X			X			X	X	X	
Urinalysis 	X	X	X	X					X			X			X	X	X	
β-hCG 	X																	
Urine Pregnancy Test 	X	X	X	X					X			X			X	X	X	
HIV/Hepatitis B,C	X																	
ALS evaluation procedures																		
ALSFRS-R	X	X	X	X	X	X	X	X	X	X	X	X	X	X	X	X	X	
SVC	X	X		X					X			X			X	X	X	
HHD		X		X					X			X			X	X	X	
ALSAQ-40	X								X							X		
ECAS		X							X						X			
EQ-5D-5L	X			X					X			X			X	X	X	
VAS		X		X					X			X			X	X	X	
Cost questionnaire	X			X					X			X			X	X	X	
King's staging system and MiToS	X			X					X			X			X	X	X	
PK																		
Blood sampling for FAB122 	X 	X 														X 	X 	
Blood sampling for riluzole 	X	X																
ALS biomarkers																		
Blood sampling for biomarkers 		X	X		X				X			X			X	X	X	
Urine collection for biomarkers 		X	X		X				X			X			X	X	X	
Future Biomedical Research																		

	Screening	Baseline	Treatment period															
	(-12/-2 days)	V1 D1 W0	V2 D28 W4 ±3D	T1 D56 W8 ±4D	V3 D84 W12 ±3D	T2 D112 W16 ±4D	T3 D140 W20 ±4D	V4 D168 W24 ±7D	T4 D196 W28 ±7D	T5 D224 W32 ±7D	V5 D252 W36 ±7D	T6 D280 W40 ±7D	T7 D308 W44 ±7D	V6/EoT D336 W48 ±7D	V7 D420 W60 ±7D	V8  D504 W72 OR EoT 		
Blood sampling for genotyping for FBR (if consented)		X																
Blood sampling for RNA and serum collection for FBR (if consented)		X		X				X			X			X	X	X		
CSF sampling for FBR (if consented) 		X		X				X										

V=visit; T= telephone call; EoT = End of Trial; W=Week, D=Day

\*First dosing

1. If a patient is withdrawn from the study or discontinues study treatment, will be asked to return to the clinic and the procedures as depicted for the End-of-Trial visit will need to be done. The first 100 patients (1/3 of the total study population) will continue study participation until week 72 (Visit 8), or until reaching an intercurrent event. For all other patients (2/3 of the study population) the end of the study will be the week 48 (visit 6) of each patient (or an intercurrent event).
2. If a patient does not participate in the extended follow-up study the End of Trial (EoT) visit will take place between 1 and 14 days after treatment cessation. If a subject roll over to the extended treatment study, treatment is to be continued until the EoT visit. The EoT visit should also be performed 7-14 days after study termination in case of withdrawal or early termination of the study.
3. β-hCG in plasma and urine pregnancy test should only be performed in women of childbearing potential.
4. Possible peripheral nerve dysfunction (= sensory or motor symptoms), diminished or absent reflexes (compared with baseline examination), sensory abnormalities (e.g. numbness or tingling) or weakness on neurological examination) will be monitored during the study. In case a subject experiences clinical signs or symptoms at home, subjects will be asked to contact the clinic.
5. The DSMB will assess the results of the NCS for the first enrolled 60 patients (about 40 active and 20 placebo). The NCS will be conducted for the first enrolled 60 patients at screening, and on weeks 4, 12, and 24. Then according to the evaluation by the DSMB, one of the following options will be performed: 1) If no neurological concerns are observed, the study will continue with one additional NCS at week 48 for the first 60 patients. Then for the next enrolled patients, one NCS will be performed at Screening and another one at week 48. Additional NCS(s) could be performed between Screening and week 48 if any abnormality is detected by the neurological examination or any suggesting symptoms of neuropathy are reported by the patient. 2) If NCS show signs of neurological damage, intensive NCS monitoring will continue for all patients at Screening and on weeks 4, 12, 24, 36, 48, 60, and 72.
6. Hematology: hematocrit, hemoglobin, RBC (red blood cell count & parameters), WBC (white blood cell count inclusive differential count), platelet count. Biochemistry: total protein, alkaline phosphatase, AST (aspartate transaminase), ALT (alanine transaminase), GGT (Gamma-glutamyl transpeptidase),

7. Vitamin B6 levels will be monitored and, if necessary, supplementation of vitamin B6 (pyridoxine (100 mg/day)) will be prescribed.
8. Urinalysis: Blood, Glucose, Protein, Specific gravity, Ketone, pH, Nitrite, Leukocytes, Bilirubin, Urobilinogen, Microscopic exam, if abnormal results are noted.
9. Blood sampling for FAB122 PK analysis will be done in ~90 subjects in selected sites. Of those ~30 subjects will participate in a PK profiling sampling schedule and the additional ~60 subjects will participate in a population PK sampling schedule. Sampling schedule for PK profiling: pre-dose and 15 min, 30 min, 1, 1.5, 2, 4 hrs., and 6hrs. after the FAB122 morning dose. The pre-dose sample may be collected within 30 minutes prior to dosing, the samples taken 15 and, 30 min post dosing samples should be taken within ±2 minutes of the scheduled time, the 1 hr. post dosing sample within ±5 minutes, the 2-hour sample within ±10 minutes and the 4 hr. and 6hr. sample within ±20 minutes of the scheduled time. The time of sampling will be accurately recorded. Sampling schedule for population PK: (1) pre-dose (within 1 hour prior to dosing), (2) within 5- and 30-minutes post dosing, (3) 1 hour and (4) 1.5 hour after the second PK sample was taken.
10. Blood sampling for the determination of riluzole concentration will be done in the subjects included in FAB122 population PK sampling in baseline and week 4 (~90 subjects) at (1) pre-dose (within 1 hour prior to dosing), (2) within 5- and 30-minutes post dosing, (3) 1 hour and (4) 1.5 hour after the second PK sample was taken. In case of discontinuation of a subject, due to safety reasons or early termination of the study, a PK sample for determination of the FAB122 concentration is to be taken in those sites where FAB122 sampling is operational. The clock time and time after last dosing is to be noted in the CRF.
11. Blood biomarkers: neurofilament light chain (NFL). Serum creatinine and serum creatine kinase will be measured in biochemistry lab testing.
12. Urine biomarkers: 8-hydroxy-2'-deoxyguanosine (8-OhdG), extracellular domain of neurotrophin receptor p75 (p75ECD).
13. Optional CSF sampling will be performed (if consented) in about 30 patients at baseline, week 12, and week 24. Lumbar Puncture for CSF sampling is an aseptic procedure which needs standard bedside aseptic procedures with no-touch technique, sterile drapes and use of chlorhexidine or an equivalent antiseptic. Local anaesthesia with small amount of lidocaine can be infiltrated. A right-handed practitioner should position the patient in the left lateral decubitus position, with the vertebrae in line with the horizontal plane and the head in a neutral position and the knees flexed, also setting position could be applied if seemed by the practitioner. The bony landmark is the L4 spinous process and the L3/L4 interspace is recommended. Atraumatic 22-gauge needle could be used, however smallest diameter needle with which the practitioner can confidently perform the procedure avoiding an increased number of attempts should be chosen. 10 ml CSF sample will be drawn at each time point. After the procedure, a small sterile dressing is placed on the site and the patient can mobilise as soon as it is comfortable to do so. Regular analgesics such as paracetamol could be prescribed.
14. Only labs parameters that are abnormal in the screening visit will be re-evaluated in baseline visit.

\* In case it's necessary, NCS assessment can be performed during the baseline visit, provided the approval from the central reader are available prior to randomization.

### **3 SUBJECTS FOR ANALYSIS**

#### **3.1 Analysis populations**

##### **3.1.1 Intent-to-treat (ITT) Analysis Set**

The ITT analysis set consists of all randomized patients. The ITT population will be used for the analysis of efficacy variables, and statistical analysis will be done “as randomized”.

##### **3.1.2 Modified Intent-to-treat (mITT) Analysis Set**

The mITT analysis set includes all patients who were randomized for this study and received at least 1 dose of investigational product regardless of any protocol deviation. The mITT population will be used for the analysis of efficacy variables, and statistical analysis will be done “as randomized”. The mITT is considered the primary analysis population.

##### **3.1.3 Per protocol (PP) Analysis Set**

The PP population includes a subset of the mITT population. Patients with major protocol deviations that might impact the primary endpoint will be excluded from this population. These deviations will be determined before database lock and unblinding. The PP population will be used in the analysis of efficacy variables.

##### **3.1.4 Safety (SAF) population**

The SAF population includes all randomized patients who have received at least one dose of the investigational drug, irrespective of satisfying other criteria. This population will be used for the analysis of safety and tolerability, and statistical analysis will be done “as treated”.

##### **3.1.5 Pharmacokinetics (PK) population**

The PK population includes all patients who received the investigational drug and provided evaluable PK data. The PK population will be used for the analysis of the PK assessments only.

#### **3.2 Protocol deviations**

Major protocol deviators will be identified to the extent possible by individuals responsible for data collection/compliance, and its analysis and interpretation. In the course of the study, all protocol deviations will be collected, and during the Blind Data Review Meeting (see section 3.3) the major and minor deviations and the consequences regarding the analysis populations/statistical analysis will be assessed. Any patients or data values excluded from analysis will be identified, along with their reason for exclusion. In general, outlier data will not be excluded. A dataset will be created and used for tabular/listing presentations.

#### **3.3 Blind Data Review Meeting**

The patients will be classified during the (Blinded) Data Review Meeting (BDRM) to the analysis populations using the protocol deviations. Invitees to this meeting are the Sponsor Medical Representative (CTL or delegate), the Sponsor Project Manager (PM), the Sponsor PK scientist, Julius Clinical PM, Julius Clinical Data Manager (DM) and the Certara lead statistician, but more roles can be invited if considered necessary. Input to this meeting will be supplied by the involved Data Management Department or the responsible PM at least one week in advance of the meeting: a blinded list of all protocol deviations (including missing and outlier data), with specific detailing and description regarding the deviation, preferably in excel.

This meeting will be held in a blinded manner. The goal of this meeting is to reach consensus on minor and major protocol deviations. In case of a major deviation impacting the primary or secondary endpoints, the specific patient will be excluded from the PP population, either completely or from a specific time point onwards. The meeting must be held prior to database lock and unblinding.

The decisions taken during this meeting will be documented by the PM (or a delegate as agreed) and sent for review to all parties involved as soon as possible after the meeting, but before database lock. If all parties involved agree, then the document is finalized, signed and stored before database lock by the PM.

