13. Optional CSF sampling will be performed (if consented) in about 30 patients at baseline, week 12, and week 24. Lumbar Puncture for CSF sampling is an aseptic procedure which needs standard bedside aseptic procedures with no-touch technique, sterile drapes and use of chlorhexidine or an equivalent antiseptic. Local anaesthesia with small amount of lidocaine can be infiltrated. A right-handed practitioner should position the patient in the left lateral decubitus position, with the vertebrae in line with the horizontal plane and the head in a neutral position and the knees flexed, also setting position could be applied if seemed by the practitioner. The bony landmark is the L4 spinous process and the L3/L4 interspace is recommended. Atraumatic 22-gauge needle could be used, however smallest diameter needle with which the practitioner can confidently perform the procedure avoiding an increased number of attempts should be chosen. 10 ml CSF sample will be drawn at each time point. After the procedure, a small sterile dressing is placed on the site and the patient can mobilise as soon as it is comfortable to do so. Regular analgesics such as paracetamol could be prescribed.

14. Only labs parameters that are abnormal in the screening visit will be re-evaluated in baseline visit.

\* In case it's necessary, NCS assessment can be performed during the baseline visit, provided the approval from the central reader are available prior to randomization.

In case that, due to ALS progression, the subject is not able to attend the clinic or perform specific testing such as HHD or SVC, at least ALSFRS score, adverse events and concomitant medication use will be collected (if necessary by telephone). For safety assessments, the on-site visits are key for the study. In case a subject is not able to attend the site for two consecutive visits IMP must be discontinued at the second missed visit. The patient can continue its participation in the trial, via telephonic visits to collect ALSFRS-R, Adverse Events and Concomitant Medication, as long as the subject does not withdraw consent.

The following sections provide details regarding the procedures to be performed at each study visit:

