### 11.3. Description of Statistical Methods

#### 11.3.1. Analysis Populations

- Intent-to-treat (ITT) Analysis Set: The ITT analysis set will consist of all randomized subjects.

---

- Modified Intent-to-treat (mITT) Analysis Set: The mITT analysis set will consist of randomized subjects who receive at least 1 dose of investigational product (IP) regardless of any protocol deviation. The treatment arm will be the arm to which they were randomized, regardless of what treatment they received.
- Safety Analysis Set: The safety analysis set will consist of randomized subjects and who receive at least 1 dose of IP. Subjects will be analysed according to treatment received. This population will be used for baseline characteristics and for safety data summaries
- Per-protocol (PP) Analysis Set: The PP analysis set will consist of all mITT subjects who do not have major protocol deviations that may affect the primary efficacy endpoint. These deviations will be determined before the study database will be closed.
- The PK Population will consist of all subjects who received study drug and provided evaluable PK data.

Subjects who prematurely discontinue from the study will be included in the safety population but may be excluded from the PK analysis population unless sufficient data is provided for PK evaluation. Subjects who are included in the PK population but have missing data for a particular endpoint will not be included in the analysis for that endpoint. Unused data, measurements from excluded subjects, unscheduled collections, or extra measurements, will not be included in the summaries, but will be presented in the subject listings.

The primary analysis will be performed on the modified intent-to-treat population (mITTs), i.e. all randomized patients who had at least one treatment intake. The analysis of the primary endpoint will be also assessed with the PP and ITT populations as per sensitivity analysis.

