- **Per Protocol and ITT Analysis:** This analysis will include patients from the PP and the ITT analysis sets. The same missing data imputation and ICE strategy as for the mITT analysis will be applied to these sensitivity analyses.

For presentation of descriptive statistics of efficacy data, no imputation or sensitivity analysis will be included, and data will be presented ‘as is’. All these analyses will be done on data available at the visit considered. In summary tables, the number of patients without missing data will be presented (per visit, if applicable) unless otherwise specified. In calculations of percentages, the denominator will be the number of patients in the applicable analysis population.

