## **5.6 Statistical analysis primary and secondary endpoints**

The primary analysis population is the mITT for the primary and all secondary endpoints. Analyses of the primary endpoint based on the ITT and PP will also be undertaken to provide supplementary information on efficacy. Statistical analysis on secondary endpoints will be considered explorative in nature and will only be done for the mITT.

For each of the primary and secondary endpoints descriptive statistics will be presented for original values and change from baseline values on a per-visit basis, for each treatment arm and overall. All individual primary and secondary endpoint data will be listed as well.

No multiple corrections will be applied: a hierarchical approach is used as per section 4.1 and all other endpoints are considered strictly explorative.

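### SAP 3.3 excludes patients from the per-protocol set for deviations that touch only secondary endpoints, contradicting SAP 3.1.3 and protocol 11.3.1, although the set is analysed only for the primary endpoint

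*SAP*

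**What the plan says.** Three places define who leaves the PP set.

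- Protocol 11.3.1: "The PP analysis set will consist of all mITT subjects who do not have major protocol deviations that may affect the primary efficacy endpoint".
- SAP 3.1.3: "Patients with major protocol deviations that might impact the primary endpoint will be excluded from this population".
- SAP 3.3: "In case of a major deviation impacting the primary or secondary endpoints, the specific patient will be excluded from the PP population", either entirely or from some time point on.

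SAP 3.3 is the operating text, because patients are assigned to the sets at that meeting. Its input is "a blinded list of all protocol deviations (including missing and outlier data"), and its goal is to agree which deviations are major and which minor. SAP section 6, which lists departures from the protocol, does not mention the wider rule.

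On the use of the set, SAP 5.6 says: "Analyses of the primary endpoint based on the ITT and PP will also be undertaken to provide supplementary information on efficacy". The same section confines statistical analysis of secondary endpoints to the mITT set.

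The notes after Table 1 in protocol section 6 cover the case where, because of progression, "the subject is not able to attend the clinic or perform specific testing such as HHD or SVC". ALSFRS, adverse events and concomitant medication are then still collected, by telephone if needed. SAP 5.1 treats telephone data as equal in quality to data from site visits.

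**The concern.** One analysis set has two membership rules. A patient with a major deviation that affects, say, SVC or hand-held dynamometry (HHD) but leaves ALSFRS-R intact stays in PP under SAP 3.1.3 and leaves it under SAP 3.3. PP is used to test whether the primary result is robust to deviations, so removing someone whose primary endpoint was validly measured does not serve that purpose.

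The certain consequence is that PP membership depends on which sentence is applied. The likely cost is some precision. There is also a conditional risk. The protocol itself says progression can stop patients doing SVC or HHD. If the meeting counted those gaps as major deviations, exclusion would depend on the outcome. With an effective drug, more placebo than FAB122 patients would go, and the PP difference would shrink for a reason unrelated to adherence. Blinding prevents selection by arm but not selection by progression.

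**Working it through.** **1. The texts side by side.**

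| Source | Deviation must affect |
|---|---|
| Protocol 11.3.1 | primary endpoint |
| SAP 3.1.3 | primary endpoint |
| SAP 3.3 | primary or secondary endpoints |
| SAP section 6 (declared changes) | nothing listed |
| SAP 5.6 (use of PP) | PP used for the primary endpoint; secondary endpoints in mITT only |

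The added criterion in SAP 3.3 therefore supports no planned analysis.

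**2. Reproducing the plan's own figure.** Inputs from protocol 11.2 and SAP 2.4: difference 3.0, SD 7.5, allocation 2:1, two-sided 5%, power 90%.

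Placebo n = (1.960 + 1.282)² × 7.5² × (1 + 1/2) / 3.0² = 98.5, rounded up to 99. With 198 on FAB122 the total is 297, against 300 stated. At 200/100 the standard error is 7.5 × √(1/100 + 1/200) = 0.919, and power is Φ(3.0/0.919 − 1.960) = 90.4%. The design reproduces.

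**3. Exclusions unrelated to outcome.** The documents give no count of secondary-only deviations, so the loss is an assumed range. The difference stays at 3.0 and only the standard error grows.

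| Lost from PP (assumed) | Remaining | Power |
|---|---|---|
| 0% | 300 | 90.4% |
| 5% | 285 | 88.9% |
| 10% | 270 | 87.3% |
| 20% | 240 | 83.2% |
| 30% | 210 | 78.0% |

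**4. Exclusions that follow progression (illustration only).** Protocol 11.2 takes a typical placebo decline of 12 points in 12 months. Assume normal changes with mean −12 on placebo and −9 on FAB122, SD 7.5. Assume also that a share q of patients who decline beyond a cut c is excluded. With z = (c − mean)/7.5, the mean of those kept is

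mean + 7.5 × q·φ(z) / (1 − q·Φ(z)).

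For c = −20 and q = 1:

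- Placebo: z = −1.067, Φ = 0.143, φ = 0.226; mean kept = −12 + 7.5 × 0.226/0.857 = −10.02.
- FAB122: z = −1.467, Φ = 0.071, φ = 0.136; mean kept = −9 + 7.5 × 0.136/0.929 = −7.90.
- Difference = 2.12.

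| Cut (points declined) | Removed, placebo / FAB122 (q = 1) | Difference, q = 1 | q = 0.5 | q = 0.25 | q = 0.1 |
|---|---|---|---|---|---|
| 24 | 5.5% / 2.3% | 2.53 | 2.78 | 2.89 | 2.96 |
| 20 | 14.3% / 7.1% | 2.12 | 2.62 | 2.82 | 2.93 |
| 16 | 29.7% / 17.5% | 1.66 | 2.54 | 2.81 | 2.93 |

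Neither the cuts nor the shares come from the documents. The q = 1 column is the extreme for each cut.

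**The case against.** The other side accepts the mismatch in wording but disputes its consequence. Its main arguments are these.

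- *Progression need not lead to exclusion.* A reader might infer that PP will lose patients because they progressed. The documents do not support that. SAP 3.3 requires a major deviation, and nowhere is missing SVC or HHD classed as major. The notes to Table 1 provide for exactly this case, so following them is hard to call a major deviation. Being on the meeting's input list is not exclusion. This stands: the route is possible, not established.
- *The loss cannot all be credited to the extra words.* Many secondary endpoints are built on ALSFRS-R, so deviations affecting them often touch the primary endpoint too and would count under SAP 3.1.3. This also stands: the increment due to the wording cannot be quantified from the documents.
- *Observed scores are not shown to be overwritten.* A reader might combine the time-point option with the statement "The same missing data imputation and ICE strategy as for the mITT analysis will be applied to these sensitivity analyses" and infer that collected scores are blanked and re-imputed. SAP 5.6.1 triggers placebo-based imputation for patients with no data collected after discontinuation, and SAP 5.2 says values excluded at the meeting are left out of analyses. Re-imputation is not stated. Nor is the time-point option an error: keeping data up to a deviation is a legitimate per-protocol choice.
- *The stakes are limited.* PP is supplementary, lies outside the testing hierarchy, and is settled blind before database lock. In the illustration the bias is towards a smaller effect.

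None of this removes the contradiction. That the meeting may choose sensibly does not replace a single pre-specified rule.

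**Conclusion.** The contradiction is certain and rests on the wording alone: SAP 3.3 is wider than SAP 3.1.3 and protocol 11.3.1, the change is undeclared, and the wider criterion has no analytic use. Applied as written, it can drop patients with valid ALSFRS-R from the PP check of the primary endpoint.

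The size is not known from the documents. If exclusions are unrelated to outcome, the cost is precision only, about 3 points of power at an assumed 10% loss (90.4% to 87.3%). Outcome selection arises only if the meeting grades progression-related gaps as major. In that case, under the normal model and cuts assumed above, the PP difference falls from 3.0 to about 1.7 to 2.5 when everyone beyond the cut is removed, and to between 2.5 and 3.0 when half or fewer are. The mITT primary analysis and the planned sample size are unaffected. The point should be corrected, but it does not threaten the primary conclusion.

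**What to change.** In SAP 3.3, replace the reference to primary or secondary endpoints with: *that may affect the primary endpoint (ALSFRS-R change at week 48)*. This matches the protocol's limit to patients "who do not have major protocol deviations that may affect the primary efficacy endpoint".

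Add one sentence: secondary assessments missed, or ALSFRS-R collected by telephone, under the provision in the notes to protocol Table 1 are not by themselves grounds for PP exclusion.

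The time-point option can stay. The cost is two sentences of SAP text, agreed before the blinded review meeting, with no new data and no change to the sample size or the primary analysis.
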